11.6.6 Clinical Benefit Rate (CBR)

Clinical benefit rate (CBR) response will be categorized in accordance with RECIST v1.1. CBR is defined as the percent of patients documented to have a confirmed CR, PR, or SD.

Descriptive statistics (frequency and percentage) and 95% exact Clopper-Pearson CI for CBR rate will be presented for FAS and CAE.

11.6.7 Subgroup Analyses, including Prior Clinical Benefit (PCB) and No Prior Clinical Benefit (NPCB) Endpoints

Baseline characteristics to be evaluated in subgroup analyses include most recent tumor PD-L1 expression test result indicating high versus low expression and, for cohorts that have prior PD-(L)1 checkpoint inhibitor therapy experience (i.e. Cohorts 1 through 4, and Cohorts 7 through 9) outcome of prior treatment with checkpoint inhibitor therapy, specifically prior clinical benefit versus no prior clinical benefit, defined as:

- Prior clinical benefit (PCB): RECIST-defined partial or complete response or stable disease for at least 12 weeks (-2 week window permitted for radiograph scheduling) followed by radiographic progression of disease.
- No prior clinical benefit (NPCB): does not meet criteria for PCB and has radiographic progression of disease \leq 12 weeks after initiation of treatment (+2 week window permitted for radiograph scheduling).
- Efficacy analyses will be presented descriptively per each subgroup listed above, for each cohort, as well as for all cohorts combined if deemed appropriate.

11.7 Safety Analyses

All safety summaries will be presented by cohort (including initial and contingent cohorts) and all cohorts combined. With regard to safety summaries, the term “on-treatment” is the period from first dose until either last dose + 28 days or the start of subsequent anti-cancer therapy, whichever is earlier.

11.7.1 Extent of Study Drug Exposure and Exposure Variables

Study Treatment Duration

Study treatment duration (weeks) is defined as $(\text{the last dose date} - \text{the first dose date} + 1) / 7$. Weeks on treatment will be summarized separately for each study drug.

Days on Sitravatinib

Days on sitravatinib is defined as the total number of days patient received sitravatinib, after subtracting for interruptions or drug missed, that is:

the $[(\text{latest Stop Date} - \text{the earliest Start Date captured on the Sitra Administration CRF page}) - \text{number of days with 0 mg dose} + 1]$.

Cycles Started

A patient is considered to have started a cycle if they received at least one dose of the study drug in that cycle, per the Study Drug Administration CRF page.

Cumulative Dose Received

- Cumulative dose received for nivolumab (mg) is defined as the total amount of nivolumab a patient receives during the study as recorded on the Nivolumab Administration CRF forms. Nivolumab is planned to be administered as a 240 mg intravenous infusion over 30 minutes every 2 weeks. An alternative dosing regimen of 480 mg intravenous infusion over 30 minutes every 4 weeks may be introduced during the study. Dose modifications should be accounted for in the cumulative dose received calculations.
- Cumulative dose received for sitravatinib (mg) is defined as the total amount of sitravatinib a patient receives during the study, that is, $\text{Sum of } [(\text{Stop date} - \text{Start date} + 1) \times \text{Total Dose (mg per administration)} \times \text{Dose Frequency}]$ as recorded on the Sitravatinib Administration CRF forms. Dose modifications should be accounted for in the cumulative dose received calculations

- Cumulative dose received for pembrolizumab (mg) is defined as total amount of pembrolizumab a patient receives during the study as recorded on the Pembrolizumab Administration CRF forms. Pembrolizumab is planned to be administered as 200 mg intravenous infusion every 3 week.
- Cumulative dose received for enfortumab is defined as total amount of enfortumab a patient receives during the study as recorded on the Enfortumab Administration CRF forms. Enfortumab is planned to be administered as 1 mg/kg infusions on Days 1 and 8, every 3 weeks for combination regimine dose level “-1²” in Cohort 9. Enfortumab is planned to be administered as 1.25 mg/kg infusions on Days 1 and 8, every 3 weeks for combination regimine dose level “1” in Cohort 9.

Compliance

- Compliance is only applied to sitravatinib and is calculated as cumulative dose received (mg) / cumulative planned dose (mg) x 100, where the adjusted cumulative planned dose = (Planned dose in mg) * (study treatment duration in days - number of days on dose interruption due to AE - number of days on dose reduction due to AE) + ∑(planned reduced daily dose x number of days on dose reduction due to AE).

Dose Intensity

- Relative dose intensity for sitravatinib, nivolumab, pembrolizumab, enfortumab is defined as:
 - For sitravatinib: [cumulative dose received (mg) / cumulative planned dose (mg)] x 100, where cumulative planned dose is calculated as the starting daily dose multiplied by the study treatment duration in days, which does not take into account dose reduction or interruption.
 - For nivolumab: [cumulative nivolumab dose received (mg)] / [cumulative planned nivolumab dose (mg)] x 100, where cumulative planned dose is:

$$\text{round} \left(\frac{\text{duration of nivolumab in weeks} + 2 \text{ weeks}}{2 \text{ weeks}} \right) \times 240 \text{ mg}, \text{ for patients who received 240 mg as last dose}$$

$$\text{round} \left(\frac{\text{duration of nivolumab in weeks} + 4 \text{ weeks}}{2 \text{ weeks}} \right) \times 240 \text{ mg}, \text{ for patients who received 480 mg as last dose}$$

Duration of nivolumab is last dose of nivolumab – first dose of nivolumab in weeks.

- For pembrolizumab: [cumulative dose received (mg) / cumulative planned dose (mg)] x 100, where cumulative planned dose is calculated as

$$\text{round} \left(\frac{\text{duration of pembrolizumab in weeks} + 3 \text{ weeks}}{3 \text{ weeks}} \right) \times 200 \text{ mg}$$

Duration of nivolumab is last dose of nivolumab – first dose of nivolumab in weeks.

- For enfortumab: [cumulative dose received (mg) / cumulative planned dose (mg)] x 100, where cumulative planned dose is calculated as:

$$\text{round} \left(\frac{\text{duration of enfortumab in weeks} + 3 \text{ weeks}}{3 \text{ weeks}} \right) \times \min(\text{starting dose} \times \text{baseline weight (kg)}, \text{maximum dose}) \times 2 \text{ (Day 1 and Day 8)}$$

Duration of enfortumab is last dose of enfortumab – first dose of enfortumab in weeks.

Descriptive statistics will be provided separately for each study drug, for the duration of exposure (weeks), the total number of cycles started, number of days on sitravatinib, cumulative dose received (mg) and absolute and relative dose intensities as well as compliance.

Number and percentage of patients with at least 1 dose reduced and reason for dose reduction (only for sitravatinib), at least 1 dose interrupted and reasons for dose interruption will be presented separately for each study drug.

Information regarding patients' dosing regimens will be listed separately for each study drug.

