5.7.3 Concomitant Surgery or Radiation Therapy

The use of surgery to manage cancer lesions during study treatment is discouraged. The impact of sitravatinib on wound healing has not yet been characterized. For patients with bone involvement, any foreseeable need for palliative radiotherapy should be addressed before study entry, if possible and clinically appropriate (e.g., bone lesions at risk for spontaneous micro-fractures or painful lesions). However, these treatments may be used in cases where it is medically necessary.

In the event that major surgery is needed during study treatment, the patient should, if possible, interrupt dosing with sitravatinib 2 weeks in advance of the surgery and resume dosing 2 weeks after the surgery.

If radiotherapy is required, the Sponsor will provide guidance on duration of sitravatinib interruption.

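### The sitravatinib compliance formula excuses only AE-related holds, so a patient who follows the protocol's surgery or radiotherapy hold and then resumes is reported below 100%

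*SAP*

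**What the plan says.** SAP Section 11.7.1 defines two sitravatinib measures that share a numerator, the cumulative dose received.

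- **Compliance.** "Compliance is only applied to sitravatinib and is calculated as cumulative dose received (mg) / cumulative planned dose (mg) x 100". The planned dose is adjusted: the full daily dose is multiplied by "study treatment duration in days - number of days on dose interruption due to AE", less AE-related reduction days. Those reduction days are then added back as "planned reduced daily dose x number of days on dose reduction due to AE".
- **Relative dose intensity.** The planned dose is the starting daily dose times treatment duration, "which does not take into account dose reduction or interruption".

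The same section fixes duration ("Study treatment duration (weeks) is defined as") as last dose date minus first dose date plus 1, divided by 7. A gap followed by resumption therefore lies inside it.

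Protocol Section 5.7.3 covers holds that need not arise from an AE. A patient having major surgery "should, if possible, interrupt dosing with sitravatinib 2 weeks in advance of the surgery and resume dosing 2 weeks after the surgery". For radiotherapy, "the Sponsor will provide guidance on duration of sitravatinib interruption". Protocol Section 5.1.3 also foresees interruption for reasons other than toxicity, with resumption at the same dose.

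**The concern.** The AE adjustment shows what compliance is for: days on which the patient was meant to be off drug, or on less of it, should not count as missed doses. Relative dose intensity is the measure that deliberately counts them. The surgery and radiotherapy holds in Protocol Section 5.7.3 are equally directed, but the compliance formula treats them as non-adherence.

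Two things follow. Reported compliance is too low for a patient who did what the protocol asked. And the same conduct scores differently according to the reason recorded for the hold. For a patient whose only gap is such a hold, compliance and relative dose intensity become the same number, so the pair no longer separates adherence from delivered dose for that patient.

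**Working it through.** The plan states no compliance figure to reproduce, so the formula is applied directly. The adjusted planned dose given in SAP 11.7.1 is taken as the denominator of the compliance ratio.

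**Inputs**

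- Daily dose d: 120 mg free base or 100 mg malate (Protocol 5.1.3). It cancels from the ratio when there is no dose reduction.
- Duration D in days: last dose − first dose + 1 (SAP 11.7.1). The values 84, 112, 168 and 336 are assumptions.
- Surgery hold h: two weeks before plus two weeks after, nominally 28 days, or 27 to 29 depending on how the end days are counted (Protocol 5.7.3).
- Radiotherapy hold: length not stated; 7 and 14 days are used as assumptions.
- All other doses taken, no dose reduction, hold not coded as AE, dosing resumed.

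**Formulas**

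- Dose received = d × (D − h)
- SAP planned dose for compliance = d × (D − 0 − 0) = d × D
- Compliance = 100 × (D − h)/D
- Relative dose intensity = 100 × d(D − h)/(d × D), the same value
- Compliance if the hold is coded as AE, or if directed holds are subtracted = 100 × (D − h)/(D − h) = 100%

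**Surgery hold**

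| D (days) | h = 27 | h = 28 | h = 29 |
|---|---|---|---|
| 84 | 67.9% | 56/84 = 66.7% | 65.5% |
| 112 | 75.9% | 84/112 = 75.0% | 74.1% |
| 168 | 83.9% | 140/168 = 83.3% | 82.7% |
| 336 | 92.0% | 308/336 = 91.7% | 91.4% |

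In milligrams, at 120 mg once daily, D = 168 and h = 28: received 120 × 140 = 16,800; planned 120 × 168 = 20,160; ratio 83.3%. With the hold removed from the denominator, 16,800/16,800 = 100%.

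**Radiotherapy hold, D = 168:** 161/168 = 95.8% for 7 days and 154/168 = 91.7% for 14 days.

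**With an AE dose reduction as well** (120 mg, D = 168, surgery hold of 28 days, 56 days at 80 mg): received 120 × 84 + 80 × 56 = 14,560; SAP planned 120 × 112 + 80 × 56 = 17,920; compliance 81.25%. Relative dose intensity is 14,560/20,160 = 72.2%. The two measures differ again, but compliance still falls short of 100% because of the surgery hold alone.

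**Cohort mean.** If a fraction f of patients has one 28-day hold and D = 112, the mean falls by f × 28/112, that is f × 25 points: 0.5, 1.25 or 2.5 points for f = 2%, 5% or 10%. These fractions are assumptions; the documents give no frequency.

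**The case against.** The strongest reply is that the case is uncommon, depends on coding, and has little consequence.

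- **Rarity.** Protocol 5.7.3 discourages surgery on cancer lesions and wants foreseeable palliative radiotherapy dealt with before entry. Section 5.1.3 says permanent discontinuation should be considered once sitravatinib has been withheld for 28 or more consecutive days, and the nominal surgery hold sits at that limit. A patient who never resumes is unaffected, because the hold then falls after the last dose. This stands as a limit on frequency. It does not remove the case: Section 5.7.3 allows both treatments when medically necessary and tells the surgical patient to resume.
- **Coding.** Protocol 8.2 counts symptoms of worsening malignancy as AEs, so some of these holds could be recorded as AE-related and already be subtracted. That may be so, and the CRF reason codes cannot be seen from the documents. But a result that depends on the reason recorded is part of the problem.
- **Convention.** Any reason-based compliance measure draws a line somewhere, and no document requires a wider one. True, but the SAP's own line excuses one kind of directed hold and not another.
- **Traceability.** The SAP provides that patients with "at least 1 dose interrupted and reasons for dose interruption will be presented separately for each study drug", and it lists dosing by patient, so a low value could be traced to its cause. This softens the effect but does not correct the reported figure.
- **Reach.** The loss of separation between the two measures is complete only for a patient with no AE adjustment, as the reduction example shows. No compliance cut-off is defined, and the 80% dose rule for Cohort 9 DLT evaluability is a separate criterion.

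**Conclusion.** The point holds. As written, the formula scores a fully adherent patient with a non-AE surgery or radiotherapy hold, followed by resumption, at (D − h)/D, and nothing else in the SAP removes those days. For one patient the understatement can be large: 25 points for a 28-day hold in a 112-day course, and 8.3 points in a 336-day course. For a cohort it is likely to be small, 0.5 to 2.5 points under the assumed frequencies. These sizes depend on assumed durations and frequencies and on the hold not being coded as an AE; the direction of the error does not depend on the assumed numbers. Only a descriptive exposure summary is affected, so the rating is minor.

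**What to change.** In SAP Section 11.7.1, replace the AE-only interruption term in the compliance denominator with all protocol-directed interruption days: AE-related holds, major-surgery holds under Protocol 5.7.3, and radiotherapy holds of the length the Sponsor advised. Keep doses missed for any other reason in the denominator. Leave the AE reduction term and relative dose intensity unchanged.

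The cost is one term in one formula. The SAP already plans to present reasons for interruption by drug, but the documents do not show whether surgery and radiotherapy are separate reason codes, so the sponsor should confirm that they can be identified. The change fits the amended SAP that SAP Section 5.0 foresees before database lock.

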5.4.3 Administration

Dosing is based on patient weight. Enfortumab will be administered at mg/kg doses based on the patient's actual body weight at Cycle 1 Day 1. For on-study dosing, the dose must be adjusted if the patient's weight changes by $\geq 10\%$ from their Cycle 1 Day 1 weight, or if enfortumab dose modification criteria (see Section 5.4.4) are met. Other dose adjustments for changes in body weight $<10\%$ are permitted per institutional standard. For patients who weigh > 100 kg, the dose will be calculated based on 100 kg weight. Institutional dose rounding rules may be applied to this protocol, but otherwise, doses of the investigational product will be rounded to the nearest milligram.

Enfortumab (PADCEV) will be administered in this study as an intravenous infusion over approximately 30 minutes (± 5 minutes) at the selected dose level (see Appendix 9) on Days 1, and 8 of a 21-day cycle, at the discretion of the Investigator and in accordance with the current [PADCEV US Prescribing Information](#). Note: enfortumab should be administered at least 30 minutes after pembrolizumab.

Patients will receive enfortumab administration only if their laboratory results of blood drawn within 24 hours prior to dosing meets the following study drug administration laboratory criteria:

- Blood glucose ≤ 250 mg/dL.

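### The enfortumab dose-intensity denominator does not fit a Day 1/Day 8 schedule: a last Day 8 dose 4 or more days late is charged a cycle that never started, and a last Day 1 dose is charged a full cycle

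*SAP*

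**What the plan says.** SAP 11.7.1, under Dose Intensity, gives this definition: "For enfortumab: [cumulative dose received (mg) / cumulative planned dose (mg)] x 100, where cumulative planned dose is calculated as" a product of three terms. They are round((duration in weeks + 3)/3), the smaller of starting dose times baseline weight and the maximum dose, and a factor of 2 labelled Day 1 and Day 8. The duration is defined just below: "Duration of enfortumab is last dose of enfortumab – first dose of enfortumab in weeks".

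Protocol 5.4.3 places the infusions on "Days 1, and 8 of a 21-day cycle".

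The other antibodies are treated differently in the same section. The nivolumab formula has two branches, chosen by the size of the last dose. The pembrolizumab formula has the same rounded term as enfortumab, but with one 200 mg dose per cycle. SAP 11.7.1 also counts a cycle as started once at least one dose has been given in it.

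**The concern.** Adding three weeks to the first-to-last interval and dividing by three counts infusions correctly when there is one per cycle, on Day 1. Enfortumab has two per cycle, unevenly spaced. The formula always charges whole pairs and does not ask whether the last dose was Day 1 or Day 8. A last Day 8 dose already sits a third of a cycle past Day 1, so a modest delay carries the argument past the rounding point.

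At stake is how Cohort 9 exposure reads. Intensity is summarised by drug, and the shortfall is largest in patients with few cycles. A reader comparing the three agents could take a rounding effect for enfortumab under-dosing.

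Delays are foreseeable. Protocol 5.4.3 makes each infusion conditional on a recent glucose result: "Patients will receive enfortumab administration only if their laboratory results of blood drawn within 24 hours prior to dosing" must meet a stated limit. That section does not say whether an infusion not given on the day is postponed or omitted, so the frequency of late doses cannot be estimated from the documents.

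**Working it through.** **Inputs.** The formula and duration are from SAP 11.7.1. The schedule (two infusions per 21 days) is from Protocol 5.4.3. The Day 8 window of ±2 days is from Table 3 of both documents. Every infusion is assumed to be given in full at the planned mg, so mg cancels and only dose counts matter. The documents state no intensity value, so there is no figure to reproduce.

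**Formula in days.** With d = days from first to last enfortumab dose, planned doses = 2 × round((d/7 + 3)/3) = 2 × round(d/21 + 1).

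**Check, last dose on an on-time Day 8 of cycle k.** d = 21(k-1) + 7, so the argument is k + 1/3, which rounds to k. Planned 2k, received 2k: 100%.

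**Last Day 8 dose late by t days.** The argument is k + 1/3 + t/21. It rounds up when t/21 ≥ 1/6, that is t ≥ 3.5, so from 4 whole days for every k. Planned becomes 2k + 2 against 2k received, so intensity is k/(k+1). For comparison, an unrounded time-based denominator is 2 × (d + 14)/21, which gives 21k/(21k + 4) at t = 4.

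| k | Received | Planned (SAP) | SAP, 4 days late | Unrounded, 4 days late |
|---|---|---|---|---|
| 1 | 2 | 4 | 50.0% | 84.0% |
| 2 | 4 | 6 | 66.7% | 91.3% |
| 3 | 6 | 8 | 75.0% | 94.0% |
| 4 | 8 | 10 | 80.0% | 95.5% |
| 5 | 10 | 12 | 83.3% | 96.3% |

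At k = 10 the SAP formula gives 20/22 = 90.9%.

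The step for k = 2: at d = 31, 31/21 + 1 = 2.48, which rounds to 2, so 4 planned and 100%. At d = 32, the argument is 2.52, which rounds to 3, so 6 planned and 67%.

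The general treatment-duration definition in SAP 11.7.1 adds one day. Used here, it would bring the threshold down to 3 days.

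Lateness is measured from the first dose, so slippage accumulates. Cycle 2 Day 1 given 2 days late, then Day 8 given 2 days late relative to that Day 1, makes d = 21 + 2 + 7 + 2 = 32. Each visit is within ±2 days if the Day 8 window runs from the actual Day 1.

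**Last dose on Day 1 of cycle k.** d = 21(k-1), the argument is exactly k, and planned is 2k against 2k-1 due and received:

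- k = 1: 1/2 = 50%
- k = 2: 3/4 = 75%
- k = 3: 5/6 = 83.3%
- k = 4: 7/8 = 87.5%
- k = 10: 19/20 = 95%

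If that last Day 1 dose is itself 11 or more days late, the argument is at least k + 11/21 and a further cycle is charged: 3/6 = 50% at k = 2 and 5/8 = 62.5% at k = 3.

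**Pembrolizumab, same patient.** With the last dose on Day 1 of cycle k, round((3(k-1) + 3)/3) = k planned and k received: 100%. (The SAP's duration line under pembrolizumab names nivolumab; I read it as pembrolizumab.)

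**The case against.** **The Day 1 case is a stated convention.** The factor of 2 is labelled with both days, and the DLT-evaluable definition (Protocol 9.3.7, SAP 8.9) speaks of two planned enfortumab doses in Cycle 1. On that reading a patient who stops after one infusion received half of what was planned. This stands: a reader might call the Day 1 result an arithmetic error, and the documents do not support that. What remains is the inconsistency with pembrolizumab. The convention also cannot excuse the late Day 8 case, where k cycles were started under the SAP's own rule and k + 1 are charged.

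**A late dose is a real loss of intensity.** True, and some reduction is fair. The unrounded figures put a 4-day delay at 84% to 96% for k = 1 to 5, so most of the fall to 50% to 83% comes from rounding. Nivolumab and pembrolizumab also round, but without a Day 8 dose sitting near the step.

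**A 4-day delay in Cycle 1 is outside the ±2-day window.** Correct for Cycle 1. Later cycles can get there through accumulated slippage.

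**The metric decides nothing.** Correct. Escalation follows mTPI-2 on DLTs (Protocol Appendix 9, SAP 7.1.5.5), and DLT evaluability uses doses taken. The SAP covers a lead-in of up to 30 patients, and its Figure 1 note says the Cohort 9 expansion and Cohort 10 will not open. Cumulative dose, interruptions with reasons and dosing listings are reported alongside.

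**Conclusion.** The formula is wrong as written, in a descriptive exposure metric only. The clear defect is the late last Day 8 dose: from 4 days late the denominator includes a cycle that never started, and intensity falls from 100% to k/(k+1). The last Day 1 result, (2k-1)/2k, is a whole-cycle convention that makes enfortumab not comparable with pembrolizumab.

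Two stronger readings are tempting. One is that fully dosed patients in general show 50% to 83%. That range covers only last Day 1 doses in cycles 1 to 3 and late last Day 8 doses in cycles 1 to 5. Both effects fade (95.0% and 90.9% at cycle 10), and an on-time last Day 8 dose reads 100%. A patient who stops after Day 1 is also better described as having received every infusion due by that date. The other is that dose selection is affected. Escalation does not use this metric, and neither document gives it a role in choosing the recommended doses.

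The figures assume full-dose infusions and duration as last minus first date. How many patients would be affected cannot be derived from the documents.

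**What to change.** Replace the rounded count with N, the number of scheduled infusions up to and including the last dose, taken from the CRF cycle and day of that dose:

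- last dose on Day 1: N = 2 × (cycle - 1) + 1
- last dose on Day 8: N = 2 × (cycle - 1) + 2

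Planned dose = N × min(starting dose × baseline weight, maximum dose). This assumes the enfortumab CRF page identifies cycle and day.

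If dates must be used, allow for the ±2-day window: N = 2 × floor((d + 2)/21) + 1 + (1 if (d + 2) mod 21 ≥ 7, else 0). Without the 2-day allowance, compliant early doses exceed 100%: d = 5-6, 19-20 and 26-27 give 2/1 = 200%, 3/2 = 150% and 4/3 = 133%. Dates remain second best. For example, d = 26 could be Cycle 2 Day 8 two days early or Cycle 2 Day 1 five days late; the rule counts 4 for both.

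If the sponsor prefers the whole-cycle convention, use 2 × the number of the cycle containing the last dose, so no unstarted cycle is charged. State that patients whose last dose is on Day 1 will read below 100%.

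The cost is one SAP formula and its program. The downside is that a scheduled-infusion count does not penalise delay, and a patient who stops after Cycle 1 Day 1 reads 100%. Delays and early stops should therefore be read from the interruption summaries (SAP 11.7.1) and the discontinuation reasons by drug (SAP 11.1), which are already planned.

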11.3 Demographic and Baseline Characteristics

Demographic and baseline data will be summarized descriptively by cohort and all cohorts combined for the initial and contingent cohorts for the Safety population. For continuous variables, descriptive statistics will include the mean, STD, median, Q1, Q3, and range. For categorical variables, descriptive statistics will include the number and percent.

The term “baseline” is defined as the last pre-dose assessment, (includes screening and Cycle 1 Day 1 pre-dose assessment which would represent a 29-day window), unless otherwise specified. Unscheduled visits assessments preceding C1D1 will be also considered for baseline. If assessment time is missing and there is no way to determine if the assessment occurred before or after study drug administration, Cycle 1 Day 1 assessments will be considered for baseline.

Demographic variables to be summarized include gender, reproductive status for female, race, ethnicity, age (years), baseline weight (kg), baseline height (m), baseline Eastern Cooperative Oncology Group (ECOG) status, and smoking history. Age is calculated from date of informed consent to date of birth.

Primary disease history will be tabulated for the Safety population and will include the summary statistics (count and percentage) for Disease Location (Renal Pelvis, Ureter, Bladder, or Urethra), disease stage (Unresectable Locally-Advanced or Metastatic), and Clinical Stage (III, IIIA, IIIB, IV, IVA, IVB, Stage unknown).

Demographic, primary disease history, and prior primary disease treatment data will be listed by patient.

Prior primary disease treatment (systemic therapies including platinum therapies and checkpoint inhibitors; radiotherapy, and surgery) will be tabulated for the Safety population and include the summary statistics (count and percentage) for the following:

- Prior platinum therapy - Platinum agent received (Cisplatin, Carboplatin, Other); Setting (Metastatic, Peri-operative); Disease Progression (Yes, No); Ineligible for platinum-based chemotherapy (Yes, No);
- Prior systemic therapy - Type (Neo-adjuvant or Adjuvant, Advanced Disease Treatment Regimen, Other);
- Prior checkpoint inhibitor – (Nivolumab, Pembrolizumab, Durvalumab, Atezolizumab, Avelumab, Other); Best Overall Response to prior Checkpoint inhibitor (CR, PR, SD, PD);
- Prior antibody drug conjugate – antibody drug conjugate received (Enfortumab Vedotin, Sacituzumab Govitecan);

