11.7.5 Vital Signs

Clinically significant findings noted during screening will be reflected on the medical history CRF, while those noted during study treatment will be collected on the AE CRFs. The following vital signs will be summarized: pulse rate (beats/min), systolic blood pressure (SBP; mmHg), diastolic blood pressure (DBP; mmHg), body temperature (C), Height (cm) and weight (kg). Height will be recorded at screening only.

Vital signs and change from baseline will be summarized. All vital signs and change from baseline through the last Cycle will be summarized by cohort and all cohorts combined. This will include a summary of the maximum and minimum values observed while the patient was on treatment and change from baseline to that observed value.

Potentially clinically important vital sign results will be summarized separately. These criteria are defined as increases in blood pressure and weight changes:

- SBP (≥ 160 mmHg, ≥ 180 mmHg, ≥ 200 mmHg)
- DBP (≥ 100 mmHg, ≥ 120 mmHg)
- Weight increased $\geq 5\%$ from baseline
- Weight decreased $\geq 10\%$ from baseline

All vital signs will be listed.

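### The enfortumab dose-intensity denominator stays at baseline weight, while the protocol requires the mg dose to follow weight once it has changed by 10% or more

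*SAP*

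**What the plan says.** SAP 11.7.1 defines relative dose intensity for enfortumab as cumulative dose received over cumulative planned dose, times 100. The numerator is what was actually given: "Cumulative dose received for enfortumab is defined as total amount of enfortumab a patient receives during the study". The denominator is a number of cycles, times the smaller of (starting dose × "baseline weight (kg")) and a maximum dose, times two for Days 1 and 8. Nothing in it refers to weight after baseline.

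SAP 11.3 says that baseline "is defined as the last pre-dose assessment", and this can be the Cycle 1 Day 1 pre-dose value. Protocol 5.4.3 starts dosing from the patient's "actual body weight at Cycle 1 Day 1", so the two documents can agree on the starting weight.

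They diverge afterwards. Under Protocol 5.4.3, "the dose must be adjusted if the patient's weight changes by" 10% or more from the Cycle 1 Day 1 value. Recalculation for smaller changes is optional: such adjustments "are permitted per institutional standard". For patients above 100 kg, "the dose will be calculated based on 100 kg weight". The SAP formula carries the cap through its maximum-dose term but not the recalculation rule.

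**The concern.** Relative dose intensity should show how much of the assigned treatment was delivered. For a drug assigned in mg/kg, a patient whose mg dose is recalculated at an unchanged mg/kg has had the full assigned treatment. Protocol 5.4.3 treats a weight change and the dose-modification criteria of Section 5.4.4 as separate reasons to change the mg amount, and only the second moves a patient down the mg/kg levels of Table 7. The SAP formula cannot distinguish them: either one lowers the numerator against a fixed denominator.

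What is at stake is the reading of one exposure summary. SAP 11.7.1 tabulates dose reductions and their reasons for sitravatinib only, so the enfortumab dose intensity is the planned summary statistic most likely to be read as showing how well that drug's dose was maintained.

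**Working it through.** Neither document states a dose-intensity figure, so there is none to reproduce. The check applies the SAP formula to a patient dosed as Protocol 5.4.3 directs.

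**Inputs from the documents**
- Planned mg = round((duration in weeks + 3)/3) × min(starting mg/kg × baseline kg, maximum dose) × 2, with duration = last dose − first dose (SAP 11.7.1).
- Maximum dose 125 mg at 1.25 mg/kg and 100 mg at 1.0 mg/kg (Protocol Table 7). Both equal the level times 100 kg, so the cap is consistent between documents.
- Recalculation is mandatory at a change of 10% or more and optional below that (Protocol 5.4.3).

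**Assumptions, not in the documents:** 80 kg at baseline; 1.25 mg/kg; six cycles; every Day 1 and Day 8 dose given at full mg/kg; last dose on Day 8; changed weight in force from Cycle 3.

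**Denominator.** Duration = 5 × 3 + 1 = 16 weeks. (16 + 3)/3 = 6.33, which rounds to 6. Planned = 6 × min(1.25 × 80, 125) × 2 = 6 × 100 × 2 = 1200 mg. With no weight change, received = 12 × 100 = 1200 mg, or 100%.

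**Received dose: four doses at 100 mg, then eight at the changed amount**

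| Situation from Cycle 3 | Weight | mg per dose | Received (mg) | Dose intensity |
|---|---|---|---|---|
| 10% loss | 72 kg | 90 | 400 + 720 = 1120 | 93.3% |
| 15% loss | 68 kg | 85 | 400 + 680 = 1080 | 90.0% |
| 20% loss | 64 kg | 80 | 400 + 640 = 1040 | 86.7% |
| 10% gain | 88 kg | 110 | 400 + 880 = 1280 | 106.7% |
| Reduction to 1.0 mg/kg, weight unchanged | 80 kg | 80 | 400 + 640 = 1040 | 86.7% |

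**Range.** Over four, six or eight cycles, with the loss starting at Cycle 2 or 3, a 10% loss gives 91.3% to 95.0%, a 15% loss 86.9% to 92.5%, and a 20% loss 82.5% to 90.0%. The percentages are the same at 1.0 mg/kg.

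**Where the effect shrinks or vanishes** (same six cycles)
- A 9% loss without recalculation stays at 100%. If the site recalculates, 80 × 0.91 = 72.8 kg gives 91 mg, and (400 + 728)/1200 = 94.0%.
- 120 kg falling to 108 kg stays at 125 mg per dose, so 100%.
- 105 kg falling to 94.5 kg gives 118.125 mg, and (500 + 945)/1500 = 96.3%.

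**With the weight in force in the denominator,** the 10%-loss patient has 1120/1120 = 100.0%.

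The last dose is placed on Day 8 to isolate weight. The formula always counts two doses in the final cycle, so stopping after a Day 1 dose lowers the result with no weight change (1100/1200 = 91.7% at six cycles). That is a separate matter.

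**The case against.** The best defence is that a fixed reference is the SAP's own convention. The sitravatinib dose intensity is also anchored to the starting dose and deliberately ignores reductions and interruptions. This does not carry over. Sitravatinib is a flat mg dose, so its planned amount does not depend on weight. Enfortumab is assigned in mg/kg, and a recalculation at the same mg/kg is not a reduction. If the sponsor does intend exposure relative to baseline-weight dosing, the SAP should say so.

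The defence is stronger on consequence, and that part stands. A reader might infer that the mismatch undermines the choice of combination dose in Cohort 9. The documents do not support this: escalation rests on dose-limiting toxicities from Cycle 1 Day 1 to pre-dose Cycle 2 Day 1, read from the mTPI-2 table (SAP 7.1.5.5 and Appendix 2), and dose intensity has no role in it.

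A reader might also infer that weight loss and a toxicity-driven reduction cannot be told apart. That holds only for the summary figure read alone. SAP 11.7.1 lists dosing for each drug, SAP 11.7.2 lists adverse events leading to dose reduction, and SAP 11.7.5 states: "Potentially clinically important vital sign results will be summarized separately". Its criteria include a weight decrease of 10% or more from baseline, the same percentage that triggers mandatory recalculation.

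Finally, the rates of treatment-related weight decrease in Protocol 1.3.3.2 (26% with sitravatinib and nivolumab) and 1.6.3.4 (20% with enfortumab and pembrolizumab) might be taken as the share of patients affected. They cover any degree of loss under other regimens and do not show how many would cross 10%.

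**Conclusion.** The mismatch is real. Following both documents exactly, a patient who receives every enfortumab dose at the full assigned mg/kg scores below 100% after a recalculated weight loss and above 100% after a gain. Under the stated assumptions a 10% loss costs 6.7 percentage points over six cycles, and a 20% loss produces the same figure as a one-level reduction from Cycle 3. The documents give no frequency for losses of either size. A per-dose ratio (90% after a 10% loss) would overstate the effect, because the SAP quantity is cumulative and includes the doses given before the change.

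The reach is small: one descriptive summary in at most 30 lead-in patients, since SAP Figure 1 notes that the Cohort 9 expansion and Cohort 10 will not be opened. No toxicity decision, efficacy result or error rate changes. This is a minor correction worth making before the exposure tables are programmed.

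**What to change.** Reconcile the SAP 11.7.1 formula with Protocol 5.4.3. Build the planned mg for each dose as the assigned starting mg/kg times the weight in force under the protocol: the Cycle 1 Day 1 weight until a change of 10% or more, then the updated weight. Where a site recalculated earlier and the dosing weight was captured, use that weight. Cap the weight at 100 kg. Computing dose intensity in mg/kg is equivalent if it uses the same weight and cap.

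Do not simply substitute the weight measured at each visit. A 9% loss that the site did not act on would then score 100/91 = 110%, a new artefact.

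If the baseline reference is intended, the minimum is a sentence saying that the result is relative to baseline-weight dosing and is not adjusted for recalculation.

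The cost is SAP wording and a little programming. Weight is already scheduled before dosing (Protocol Table 3, footnote 4), but the documents do not show that the weight used for dosing is recorded, so optional adjustments below 10% can be handled exactly only if it is. No clinical rule needs to change.
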